5.1 Imputation rules

5.1.1 Study drug

Not applicable.

5.1.2 AE date imputation

Incomplete Start Date:

Missing day and month

- If the year is the **same** as the year of the first dosing date, then the day and month of the first dosing date will be assigned to the missing fields.
- If the year is **prior to** the year of first dosing date, then December 31 will be assigned to the missing fields.
- If the year is **after** the year of first dosing, then January 1 will be assigned to the missing fields.

Missing day only

- If the month and year are the **same** as the year and month of first dosing date, then the first dosing date will be assigned to the missing day.
- If either the year of the partial date is **before** the year of the first dosing date or the years of the partial date and the first dosing date are the same but the month of partial date is **before** the month of the first dosing date, then the last day of the month will be assigned to the missing day.
- If either the year of the partial date is **after** the year of the first dosing date or the years of the partial date and the first dose date are the same but the month of partial date is **after** the month of the first dosing date, then the first day of the month will be assigned to the missing day.
- If the stop date is not missing, and the imputed start date is after the stop date, the start date will be imputed by the stop date.

Missing day, month, and year

- No imputation is needed, the corresponding AE will be included as TEAE.
- Incomplete Stop Date:** If the imputed stop date is before the start date, then the imputed stop date will be equal to the start date.

Missing day and month

- If the year of the incomplete stop date is the **same** as the year of the last dosing date, then the day and month of the last dosing date will be assigned to the missing fields.
- If the year of the incomplete stop date is **prior to** the year of the last dosing date or prior to the year of the first dosing date, then December 31 will be assigned to the missing fields.
- If the year of the incomplete stop date is **prior to** the year of the last dosing date but is the same as the year of the first dosing date, then the first dosing date will be assigned to the missing date.
- If the year of the incomplete stop date is **after** the year of the last dosing date, then January 1 will be assigned to the missing fields.

Missing day only

- If the month and year of the incomplete stop date are the **same** as the month and year of the last dosing date, then the day of the last dosing date will be assigned to the missing day.

- If either the year of the partial date is **not equal to** the year of the last dosing date or the years of the partial date and the last dosing date are the same but the month of partial date is **not equal to** the month of the last dosing date, then the last day of the month will be assigned to the missing day.

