2.9.1 Adverse events (AEs)

Only Treatment-emergent AEs (TEAEs) will be summarized. Treatment-emergent AEs (TEAEs) are those AEs that started after the first dose of study treatment or events present prior to the first dose of study treatment but increased in severity based on preferred term and on or before last dose + 84 days.

TEAEs will be assigned to the last treatment received at the time of onset/worsening of AE. For summaries beyond treatment period 1, patients who switched from Placebo to Secukinumab will appear in both the population of patients for Placebo and Secukinumab (150 mg + 300 mg) treatment groups. If an AE occurred on the last day of treatment period 1 and the patient did not enter treatment period 2 it will be included as a TEAE in the treatment period 1.

Adverse events will also be reported according to MedDRA. The MedDRA version used for reporting the study will be described in a footnote.

Adverse events will be summarized by presenting, for each treatment group, the number and percentage of patients having any AE, having an AE in each primary system organ class and having each individual AE (preferred term). Summaries will also be presented for AEs by severity and for study treatment related AEs. If a patient reported more than one AE with the same preferred term, the AE with the greatest severity will be presented. If a particular AE 'severity' is missing, this variable will be listed as missing and treated as missing in summaries. If a patient reported more than one AE within the same primary system organ class, the patient will be counted only once with the greatest severity at the system organ class level, where applicable. Serious AEs will also be summarized.

The incidence of AEs will be presented per 100 patient years of exposure for the most frequent AEs ($\geq 2\%$ in any group) and SAEs.

Separate summaries will be provided for SAEs, other significant AEs leading to discontinuation and AEs leading to dose adjustment (including study treatment discontinuation).

A graphical display of the crude rates within system organ classes will be presented. The placebo group will be displayed with a bar whereas dots will be used for secukinumab treatment groups.

Non-treatment emergent adverse events will be summarized as well. These adverse events occurred before the first dose of the study treatment. The crude incidence rate will be provided without treatment information.

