5.1.3 Concomitant medication date imputation

Table 3 below should be used to determine whether medications are concomitant or not. If a medication is considered concomitant it should be reported in each treatment period in which it is administered. The rules below for determining if a medication is concomitant should be applied to determine if the medication is concomitant within a particular period by using the start and end dates of the treatment period rather than overall start and end dates of study medication. The phases are defined in [Section 2.1.1](#). In the event that the medication could have potentially started in either phase then it should be considered concomitant in both.

Table 4: Concomitant medication date imputation

START DATE	STOP DATE	ACTION
Known	Known	
If stop date < study med start date, assign as prior
 
If stop date \geq study med start date and start date \leq study med end date, assign as concomitant
 
If stop date \geq study med start date and start date $>$ study med end date, assign as post study

	Partial	
Impute stop date as latest possible date (i.e. last day of month if day unknown or 31st December if day and month are unknown), then:
 
If stop date < study med start date, assign as prior
 
If stop date \geq study med start date and start date \leq study med end date, assign as concomitant
 
If stop date \geq study med start date and start date $>$ study med end date, assign as post treatment

	Missing	
If stop date is missing could never be assumed a prior medication
 
If start date \leq study med end date, assign as concomitant
 
If start date $>$ study med end date, assign as post treatment

START DATE	STOP DATE	ACTION
Partial	Known	
Impute start date as earliest possible date (i.e. first day of month if day unknown or 1st January if day and month are unknown), then:
 
If stop date < study med start date, assign as prior
 
If stop date \geq study med start date and start date \leq study med end date, assign as concomitant
 
If stop date \geq study med start date and start date $>$ study med end date, assign as post treatment

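### Partial AE onset dates are imputed against the first dose only, so in placebo patients who switch at Week 12 secukinumab events can be credited to placebo but never the reverse

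*SAP*

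**What the plan says.** **Onset imputation (SAP 5.1.2).** Every rule for an incomplete start date refers to the first dosing date:
- Day missing, same month as first dose: "then the first dosing date will be assigned to the missing day".
- Day missing, later month: "then the first day of the month will be assigned to the missing day".
- Day and month missing, same year as first dose: "then the day and month of the first dosing date will be assigned to the missing fields".
- Day and month missing, later year: "then January 1 will be assigned to the missing fields".
- If the imputed start falls after a known stop date, "the start date will be imputed by the stop date".
- Date wholly missing: "No imputation is needed, the corresponding AE will be included as TEAE". No onset date and no treatment are specified.

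**Attribution (SAP 2.9.1).** "TEAEs will be assigned to the last treatment received at the time of onset/worsening of AE". In summaries beyond treatment period 1, patients who switched count in both the placebo and the secukinumab populations.

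**The switch (SAP 1.1).** Group 2 starts open-label secukinumab at Week 12.

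**Comparison (SAP 5.1.3).** Concomitant medication is classified with treatment-period dates. For an uncertain start the rule is: "In the event that the medication could have potentially started in either phase then it should be considered concomitant in both".

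**The concern.** For a patient who switched, the onset date alone decides whether an event appears under placebo or under secukinumab. The first dose is a sensible anchor for deciding whether an event is treatment-emergent. It does not help to decide which of two successive treatments the event belongs to, and section 5.1.2 offers no second anchor at the Week 12 injection.

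At stake are the AE tables by treatment and the exposure-adjusted incidence rates with 95% confidence intervals that section 2.9.1 plans for the entire treatment period. An attribution error that always runs from active drug to control is the unfavourable direction for a safety summary. Efficacy and the tested hypotheses are not touched.

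**Working it through.** The SAP states no figure on this point, so the rules were applied to every possible case.

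**Inputs.** Switch on Day 85, the scheduled Week 12 day (SAP Table 5-1); range Day 72 to 99, the Week 12 window. Treatment-emergent cut-off at last dose + 84 days (2.9.1); with a last dose at Week 52, Day 365, this is 365 + 84 = Day 449. Assumptions: first doses spread evenly over the 365 days of a year; onsets spread evenly over days; an onset on the switch day counts as secukinumab.

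**Direction.** For a true onset on or after the first dose, each rule returns the earliest date compatible with the recorded part. The stop-date rule can only move the onset earlier. Enumeration over all first-dose dates, three switch days, and stop dates absent or 0, 7 or 30 days after onset gave no imputed date later than the true one. No placebo event moved to secukinumab.

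**Example.** First dose 15 January 2019, switch 9 April 2019, true onset 14 April 2019. With the day missing, onset becomes 1 April and is counted under placebo.

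**Only the day missing.** If the switch falls on day d of an m-day month (d > 1), the m − d + 1 onset days from the switch to month end all go back to the first, which is placebo time. Summed over d = 2 to m this is m(m−1)/2.
- Over 12 months: 7 × 465 + 4 × 435 + 378 = 5,373.
- Per switcher: 5,373/365 = 14.7 onset days.
- Weeks 12-24 (84 days): 14.7/84 = 17.5% (15.2% to 21.0% for a switch on Day 72 to 99).
- Day 85 to 449 (365 days): 14.7/365 = 4.0%.
- Within the switch month alone: (m−1)/(m+1), for example 30/32 = 94%.

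**Day and month missing.** Let the first dose fall on day k of the year.
- k = 1 to 281: the switch is in the same year, and onsets from the switch to 31 December (282 − k days) become the first dosing date. Sum: 281 × 282/2 = 39,621.
- k = 282: the switch is on 1 January; no error.
- k = 283 to 365: the switch is in the next year, and onsets from the switch to the end of that year (647 − k days) become 1 January, before the switch. Sum: 83 × (364 + 282)/2 = 26,809.
- Total 66,430, or 66,430/365 = 182.0 onset days per switcher. Up to Day 449: 182.0/365 = 49.9% (48.1% to 51.8%).
- Weeks 12-24: 198 × 84 + 3,486 + 83 × 84 = 27,090 of 365 × 84 = 30,660, which is 88.4% (86.6% to 90.3%).

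**Reverse error if ambiguous onsets go to secukinumab instead.**
- Day missing: the placebo days earlier in the switch month number d − 1, which sum to the same 5,373. 14.7/84 = 17.5% of placebo-time onsets.
- Day and month missing, no limiting stop date: (281 × 84 + 3,486)/30,660 = 27,090/30,660 = 88.4% of placebo-time onsets.

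**The case against.** **The percentages can mislead.** They apply only to events with that kind of partial date; events with complete dates are unaffected. This stands. The SAP gives no frequency of partial dates. At these rates, one misassigned event needs about 1/0.040 = 25 secukinumab-time events with a missing day in switchers, or about 2 with day and month missing.

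**A reader might infer that placebo rates rise sharply.** Placebo exposure is short: about 82 × 84/365.25 = 18.9 patient-years if the target of 82 patients all complete Period 1, so one misassigned event is worth about 5 per 100 patient-years. Without a count of partial dates, however, the SAP supports no statement about the actual rise. Follow-up to Day 449 is also an upper case, since Period 3 is optional and non-responders are withdrawn at Week 24 (1.1).

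**A reader might infer that the randomised safety comparison is biased.** The documents do not support this. In Period 1 tables the same rules pull later onsets back in both arms, and both arms receive secukinumab from Week 12, so with similar onset patterns both gain similar numbers. The one-way error concerns summaries beyond Period 1, which already set 12 weeks of placebo against a much longer time on secukinumab and are not purely randomised comparisons.

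**The concomitant-medication rule is not a direct model.** A medication can span periods, whereas an AE has one onset and one treatment. Section 5.1.3 also uses the earliest possible start date. It does show that the SAP recognises the period boundary there and not for AEs.

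**The remedy reverses the error and does not remove it.** This is correct and must be stated with the remedy. What remains is that the present rule errs in favour of the active drug.

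**Conclusion.** The point holds as a minor one. Sections 5.1.2 and 2.9.1, applied as written, allow partial onsets in switchers to move only from secukinumab to placebo. The direction follows from the rules and needs no distributional assumption. The one exception is a switch on the first of a month, where a missing day causes no error.

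The sizes given above rest on evenly spread first doses and onsets and on follow-up to about Day 449. They are proportions of events with partial onsets in placebo-first patients, not of all events. The absolute effect on the tables cannot be calculated from the SAP. Wholly missing onsets are a separate gap: they are counted as treatment-emergent, but the attribution rule has no date to work on.

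**What to change.** Add one rule to 5.1.2. For patients who switched from placebo, if a partial or wholly missing onset could fall on or after the first open-label secukinumab injection, and any known stop date allows it, assign the event to secukinumab. Set its onset to the later of the currently imputed date and that injection date.

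State in the SAP that this is a deliberate choice to be conservative for secukinumab. It moves some placebo-time events to the active drug: about 17.5% of placebo-time onsets with the day missing, and up to about 88% with day and month missing and no limiting stop date. Wholly missing onsets in switchers would all go to secukinumab unless a stop date prevents it. Report the number of AEs whose treatment depends on the rule, so that readers can see whether it matters.

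The cost is one sentence in the SAP, one edit to the AE program and one count in the output. Secukinumab AE rates may rise somewhat. Efficacy analyses do not change.

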2.1.1 General definitions

Treatment periods

Period 1 = from first dose up to but not including Week 12 dose.

Period 2 = Week 12 dose up to but not including Week 24 dose.

Extension = Week 24 dose until Week 52.

Follow-up = After Week 52 until Week 64

Study Day 1 and other study days

The first day of administration of randomized study treatment (first dose) is defined as *Study Day 1 or Day 1*.

All other study days will be labeled relative to Day 1. For event dates on or after Day 1, study day for a particular event date is calculated as [Date of event] – [Date of first dose]+1, i.e., Day 2, Day 3, etc., will be one day, two days, etc., after Day 1, respectively. For the dates before Day 1, study day for an event date is calculated as [Date of event] – [Date of first dose], i.e., Day -1, Day -2, etc., will be one day, two days, etc., before Day 1, respectively. Duration of an event will be calculated as (Event end date – Event start date + 1).

The descriptor “Day 0” will not be used.

Screening, baseline and post-baseline definitions

Screening refers to any procedures (e.g., checking inclusion and exclusion criteria) performed prior to the date of first dose of study treatment. Per protocol, subject informed consent must be obtained prior to performing any study related activity. The date of signing informed consent is the start date of screening period. Any assessment

obtained during the screening period will be labeled screening assessment. Assessments made on Day 1 may occur before or after the randomization or the first dose.

For efficacy analyses, baseline is the last assessment (including unscheduled visits) obtained before the first dose of study treatment . All assessments obtained after the first dose of study treatment are considered as post-baseline unless otherwise specified.

For safety analyses, baseline is the last assessment (including unscheduled visits) obtained before the first dose of study treatment. All assessments obtained after the first dose of study treatment are considered as post-baseline unless otherwise specified.

Of note, re-randomization will not be used for baseline definition and only one baseline value will be defined referring to the first randomization.

Day of last dose of randomized study treatment

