Algorithms for date imputations will be provided in Appendix 5.1.2.

Exposure time-adjusted incidence rates including 95% CIs will be presented for the entire treatment period. A graphical display of the crude rates and exposure-adjusted incidence rates will be presented for all AEs and SAEs by SOC.

In addition, for the legal requirements of clinicaltrials.gov and EudraCT, 2 required tables on TEAEs which are not SAEs with an incidence greater than 2% and on treatment emergent AEs and SAEs suspected to be related to study treatment will be provided by primary SOC and PT on Safety set population.

If for the same patient, several consecutive AEs (irrespective of study treatment causality, seriousness and severity) occurred with the same primary SOC and PT:

- A single occurrence will be counted if there is ≤ 1 day gap between the end date of the preceding AE and the start date of the consecutive AE
- More than one occurrence will be counted if there is > 1 day gap between the end date of the preceding AE and the start date of the consecutive AE

For occurrence, the presence of at least one SAE/SAE suspected to be related to study treatment/non-SAE has to be checked in a block e.g., among AEs in a ≤ 1 day gap block, if at least one SAE is occurring, then one occurrence is calculated for that SAE.

The number of deaths resulting from SAEs suspected to be related to study treatment and SAEs irrespective of study treatment relationship will be provided by SOC and PT.

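### Two AE stop-date rules in SAP section 5.1.2 conflict when only the stop year is known and it is the first-dose year but not the last-dose year; one of them makes any AE with on-treatment onset a one-day event

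*SAP*

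**What the plan says.** SAP section 5.1.2, under the incomplete stop date with day and month missing, has four bullets, numbered here in printed order.

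- Bullet 1, stop year equal to the last-dose year: "then the day and month of the last dosing date will be assigned to the missing fields".
- Bullet 2, stop year before "the year of the last dosing date or prior to the year of the first dosing date, then December 31 will be assigned".
- Bullet 3, stop year before the last-dose year "but is the same as the year of the first dosing date, then the first dosing date will be assigned to the missing date".
- Bullet 4, stop year after the last-dose year: 1 January.

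A floor sits above the bullets: "If the imputed stop date is before the start date, then the imputed stop date will be equal to the start date". If only the day is missing, the stop is the last day of the month, unless month and year match the last dose, when the last dosing day is used.

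Elsewhere, section 2.1.1 says: "Duration of an event will be calculated as (Event end date – Event start date + 1", plus a closing bracket. Section 2.9.1 uses the AE end date to count occurrences for the ClinicalTrials.gov and EudraCT tables: "A single occurrence will be counted if there is ≤ 1 day gap between the end date of the preceding AE" and the start of the next one with the same primary SOC and preferred term.

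**The concern.** Bullet 3 repeats the first condition of bullet 2 and adds a restriction, so every AE under bullet 3 also falls under bullet 2. The two give different dates, and the section does not say which prevails. Two programmers following the text could derive different end dates for the same record.

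Treating bullet 3 as an exception settles the precedence but not the result. The first dosing date cannot be later than the onset of an AE that began on or after first dose, so the imputed stop never falls after the start. With the floor applied, each such AE collapses to one day whatever its true length. At stake is whether later same-term AEs are merged with the earlier one or counted separately in the registry tables.

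**Working it through.** **Inputs.** The four bullets and the floor (section 5.1.2); duration = end − start + 1 (section 2.1.1); the occurrence rule (section 2.9.1); dosing up to Week 52 (section 1.1); scheduled days for Weeks 12, 20, 48 and 52 = Days 85, 141, 337 and 365 (section 5.4). The plan gives no figure of its own to reproduce here.

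**Step 1: which combinations trigger which bullet.**

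| First-dose year | Last-dose year | Stop year | Bullets that apply |
|---|---|---|---|
| 2018 | 2018 | 2017 | 2 |
| 2018 | 2018 | 2018 | 1 |
| 2018 | 2018 | 2019 or 2020 | 4 |
| 2018 | 2019 | 2017 | 2 |
| 2018 | 2019 | 2018 | **2 and 3** |
| 2018 | 2019 | 2019 | 1 |
| 2018 | 2019 | 2020 | 4 |

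One pattern gives two answers: stop year = first-dose year < last-dose year.

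**Step 2: what the two answers do.** Illustrative dates: first dose 1 October 2018, last dose on Day 365 = 30 September 2019, stop year 2018 only.

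| AE start | Bullet 2: stop 31 Dec 2018 | Bullet 3: stop 1 Oct 2018, then floor |
|---|---|---|
| 15 Sep 2018 (before first dose) | 108 days | 17 days, cut at first dose |
| 1 Oct 2018 | 92 days | 1 day |
| 2 Oct 2018 | 91 days | 1 day |
| 15 Nov 2018 | 47 days | 1 day |
| 20 Dec 2018 | 12 days | 1 day |

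Under bullet 3 every start from 1 October to 31 December 2018 gives 1 day. An AE already present before first dose, which is treatment-emergent if it worsened, is cut at first dose instead.

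**Step 3: comparison with the missing-day rule.** For the AE starting 15 November, a stop recorded as December 2018 becomes 31 December 2018, so 47 days. Recorded as 2018 alone, it lasts 1 day under bullet 3. Losing the month takes 46 days off the event.

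**Step 4: effect on an output.** Suppose a second AE with the same SOC and preferred term starts on 10 December 2018 in that patient. Under bullet 2 the first AE ends on 31 December, after the second has begun, so there is one occurrence. Under bullet 3 it ends on 15 November, 25 days before 10 December, so there are two.

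**Step 5: how often the year pattern arises.** With a first dose on day d of a 365-day year and a last dose on Day L, the last dose falls in the next year if d + L − 1 > 365. That holds for L − 1 of the 365 possible first-dose days.

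| Last dose on | First-dose days with the pattern |
|---|---|
| Day 365 (Week 52) | 364/365 = 99.7% |
| Day 337 (Week 48) | 336/365 = 92% |
| Day 141 (Week 20) | 140/365 = 38% |
| Day 85 (Week 12) | 84/365 = 23% |

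These are shares of calendar days, and equal patient shares only if first doses are spread evenly over the year. They say how often the clash can arise, not how many AEs meet it.

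**The case against.** The best defence is that bullet 3 reads as a specific exception to a general rule, since it would have no function otherwise. What remains would then be a choice of imputed date, not a contradiction. As a reading of intent this is reasonable, but the text does not say so, and it makes the one-day result certain.

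Three further objections stand and limit the point.

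- A reader might infer that reported AE durations would be distorted. Section 2.1.1 defines event duration, but the visible text of section 2.9 plans no summary of AE duration.
- A reader might infer that AE incidence is biased. Section 2.9.1 counts an AE as treatment-emergent if it began after first dose, or was already present and then worsened, up to 84 days after last dose. Status and attribution therefore rest on onset or worsening, and patient-level incidence does not depend on the stop date.
- A reader might say that bullet 3 breaks a latest-possible-date convention for AE stops. There is none: bullet 1 uses the last dosing date and bullet 4 uses 1 January. The latest-date convention belongs to concomitant medications in section 5.1.3. The inconsistency is with bullet 2 and the missing-day rule only.

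It is also fair that 31 December has a bias of its own. It lengthens events and can absorb a separate later AE, so neither date is neutral.

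**Conclusion.** The rule is wrong as written. Bullets 2 and 3 assign two dates to one configuration without precedence, and bullet 3, if it governs, turns every AE with onset on or after first dose into a one-day event.

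The consequence is small. The clash requires a stop date with day and month both missing, a stop year equal to the first-dose year, and a last dose in a later year. The year pattern is available to nearly all patients dosed to Week 52 and to fewer early discontinuers, but the number of AEs recorded with only a stop year is not given and is assumed to be small. Among visible outputs only the occurrence counts in the two registry tables can change, and only where the same patient has a later AE with the same SOC and preferred term whose gap from the earlier one crosses the one-day limit. The documents do not support extending this to efficacy, treatment-emergent status or the percentage of patients with an AE.

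**What to change.** Delete bullet 3 from the stop-date rules for missing day and month in section 5.1.2. Bullet 2 already covers every stop year before the last-dose year, so no gap opens and each combination in the first table then has one answer. No cap at death or last contact is needed for this case, because a patient dosed in a later year was alive and in contact on that 31 December.

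A precedence statement would also end the ambiguity, but if it favoured bullet 3 the one-day result would remain.

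The cost is one deleted line and the matching line of the derivation program. The trade-off is that some events will be over-extended to the year end, and a genuinely separate same-term event later that year may be merged into the earlier one.
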